12.5.2 Safety endpoints

The safety set will be used for all safety analyses.

Safety summaries include only data from the on-treatment period. In particular, summary tables for adverse events (AEs) will summarize only on-treatment events, with a start date during the on-treatment period (treatment-emergent AEs).

The on-treatment period lasts from the date of first administration of study treatment to 30 days after the date of the last actual administration of the study treatment or the end of study, whichever is the latest.

Adverse events

All information obtained on adverse events will be summarized overall and listed by participant.

The number (and percentage) of participants with treatment-emergent adverse events (events started after the first dose of study medication) will be summarized in the following ways:

- by primary system organ class and preferred term.
- by primary system organ class, preferred term and maximum severity.

Separate summaries will be provided for study medication related treatment-emergent adverse events, death, serious treatment-emergent adverse events and other significant treatment-emergent adverse events leading to permanent treatment discontinuation.

A participant with multiple adverse events within a primary system organ class is only counted once towards the total of the primary system organ class.

12.5.3 Patient reported outcomes

Quality of Life – EQ-5D-5L

Summary statistics of EuroQol-5D-5L (EQ-5D-5L) VAS scores at each time point as well as changes from Baseline will be provided. Paired t-test or signed rank test, based on data distribution, will be used to test the difference in VAS scores at Week 48 vs Baseline.

Hospital Anxiety and Depression Scale

Descriptive statistics of HAD-A and HAD-D score at each time point with changes vs Baseline will be provided. Paired t-test or signed rank test, based on data distribution, will be used to test the difference in HAD-A and HAD-D scores at Week 48 vs Baseline.

The sub-scores, HAD-A and HAD-D, will also be displayed per class (i.e. scores ≥ 11 indicate the presence of anxious or depressive disorders; scores between 8-10 points are borderline abnormal, and scores of ≤ 7 indicate that the disorder is not present) at each time point by means of a shift table.

In addition, the prevalence of anxiety and depression will be presented on the basis of the following three criteria: as per the score on the corresponding sub-scores of the HAD questionnaire, in terms of the treatment they are receiving for anxiety/depression, and according to both criteria.

12.6 Interim analyses

An interim analysis will be conducted when 50% of the participants planned to be enrolled have completed their Week 16 visit to evaluate the reasons underlying the Investigators' choice of brolucizumab treatment regimen at Week 16. The reasons underlying the Investigator's choice of brolucizumab dosing regimen (q12w or q8w) at Week 16 among BCVA and/or IRF, SRF, sub-RPE fluid, hemorrhage and/or CRT and/or OCTA parameters and/or 3-field CFP will be descriptively summarized. A multivariate logistic regression model will also be implemented in order to evaluate which of these factors are determinants for the selection of the dosing regimen.

12.7 Sample size calculation

12.7.1 Primary endpoint(s)

[figure not shown]
The sample size calculation is based on the assumption of an expected percentage of participants who have maintained the q12w regimen up to Week 48 equal to 56%, as derived from the HAWK study, and the hypothesis of a maximum percentage of not-fluid free participants out of these q12w-regimen participants at Week 48 equal to 18%. Therefore, the percentage of responders, defined as fluid-free participants who have maintained a q12w stable regimen up to Week 48, could range between 56% to 46%.

Considering a percentage of responders of 56% and a maximum width of the 95% confidence interval of 12%, 263 patients should be enrolled. Applying the rules of thumb, with 263 patients and a percentage of responders of 56%, a maximum number of 12 covariates can be included in the multivariate regression model (Harrell, 2015). As shown in [Figure 12-1](#), the precision of the estimate remains stable around 12%, considering a percentage of responders ranging between 56% to 46%. Similar considerations can be made with a number of covariates that remains equal to 12.

Finally, to account for a screening failure rate of 12%, a total of approximately 300 participants will be screened in order to enroll 263 evaluable participants.

The sample size calculations were performed with Nquery 7.0.

Figure 12-1 Precision of the estimate scenario

13 Ethical considerations and administrative procedures

13.1 Regulatory and ethical compliance

This clinical study was designed and shall be implemented, executed and reported in accordance with the ICH Harmonized Tripartite Guidelines for Good Clinical Practice, with applicable local regulations (including European Directive 2001/20/EC, US CFR 21), and with the ethical principles laid down in the Declaration of Helsinki.

13.2 Responsibilities of the Investigator and IRB/IEC

Before initiating a trial, the Investigator/institution must obtain approval/favorable opinion from the Institutional Review Board/Independent Ethics Committee (IRB/IEC) for the trial protocol, written informed consent form, consent form updates, participant recruitment procedures (e.g., advertisements) and any other written information to be provided to participants. Prior to study start, the Investigator is required to sign a protocol signature page confirming his/her agreement to conduct the study in accordance with these documents and all of the instructions and procedures found in this protocol and to give access to all relevant data and records to Novartis monitors, auditors, Novartis Quality Assurance representatives, designated agents of Novartis, IRBs/IECs, and regulatory authorities as required. If an inspection of the clinical site is requested by a regulatory authority, the Investigator must inform Novartis immediately that this request has been made.

13.3 Publication of study protocol and results

The protocol will be registered in a publicly accessible database such as clinicaltrials.gov and as required in EudraCT. In addition, after study completion and finalization of the study report the results of this trial will be submitted for publication and posted in a publicly accessible database of clinical trial results, such as the Novartis clinical trial results website and all required

Health Authority websites (e.g. Clinicaltrials.gov, EudraCT etc.). Results from the interim analyses may be published prior to study completion.

For details on the Novartis publication policy including authorship criteria, please refer to the Novartis publication policy training materials that were provided to you at the trial Investigator meetings.

13.4 Quality Control and Quality Assurance

Novartis maintains a robust Quality Management System (QMS) that includes all activities involved in quality assurance and quality control, to ensure compliance with written Standard Operating Procedures as well as applicable global/local GCP regulations and ICH Guidelines.

Audits of Investigator sites, vendors, and Novartis systems are performed by auditors, independent from those involved in conducting, monitoring or performing quality control of the clinical trial. The clinical audit process uses a knowledge/risk-based approach.

Audits are conducted to assess GCP compliance with global and local regulatory requirements, protocols and internal SOPs, and are performed according to written Novartis processes.

14 Protocol adherence

This protocol defines the study objectives, the study procedures and the data to be collected on study participants. Additional assessments required to ensure safety of participants should be administered as deemed necessary on a case by case basis. Under no circumstances including incidental collection is an Investigator allowed to collect additional data or conduct any additional procedures for any purpose involving any investigational drugs under the protocol, other than the purpose of the study. If despite this interdiction prohibition, data, information, observation would be incidentally collected, the Investigator shall immediately disclose it to Novartis and not use it for any purpose other than the study, except for the appropriate monitoring on study participants.

Investigators ascertain they will apply due diligence to avoid protocol deviations. If an Investigator feels a protocol deviation would improve the conduct of the study this must be considered a protocol amendment, and unless such an amendment is agreed upon by Novartis and approved by the IRB/IEC and Health Authorities, where required, it cannot be implemented.

16.1 Appendix 1: Clinically notable laboratory values and vital signs

Not applicable.

16.2 Appendix 2: Liver event and laboratory trigger definitions & follow-up requirements

Not applicable.

16.3 Appendix 3: Specific Renal Alert Criteria and Actions and Event Follow-up

Not applicable.

| | |
|--|----------------------------------|
| | Statistical Analysis Plan |
| | Sponsor: Novartis |
| | Protocol: CRTH258AIT04 |

CRTH258AIT04 / NCT04774926

[figure not shown]
**One year, single arm, open label, multicenter, phase IV
study using multimodal imaging to guide disease activity
assessment through innovative early predictive anatomical
biomarkers of fluid resolution in wAMD patients treated
with brolucizumab – IMAGINE study**

| | |
|------------------------|---------------------------------|
| Authors | ██████████, Senior Statistician |
| Document status | Final version 1.0 |
| Date | 28-NOV-2023 |

[figure not shown]
| | |
|--|----------------------------------|
| | Statistical Analysis Plan |
| | Sponsor: Novartis |
| | Protocol: CRTH258AIT04 |

Document History

| Status and Version | Release Date | Change Description | Reason/Comment |
|--------------------|--------------|--|--|
| Draft Version 0.1 | 11-SEP-2023 | N.A. | N.A. |
| Draft Version 0.2 | 15-SEP-2023 | Internal Review | Internal Review |
| Draft Version 0.3 | 22-NOV-2023 | 
[REDACTED]
 
Further details included in section 4.4.1 for partial dates and in section 6.3.2.4 for patients without fluid resolution.
 
Graphical representation of CST values and a description of this parameter on patients with BCVA ETDRS score lower than 69 letters at baseline were included in section 6.3.2.2. Graphical representation of BCVA ETDRS score values was included in section 6.3.2.3 and all analysis on BCVA results repeated on patients with BCVA ETDRS lower than 69 letters at baseline.
 
Details of total number of parameters used to choose the treatment regimen and on all possible combinations were included in section 6.3.2.5 together with additional analysis on SD-OCT parameters at baseline and type of predominant CNV lesion by BCVA or CST groups based on changes at Week 12.
 
Evaluation of anxiety/depression based on treatment was deleted from section 6.3.2.6.
 
Section 1.1 was update accordingly to changes described.
 
Section 6.3.1 was updated to consider as predictor variables that reflect changes
 | 
[REDACTED]
 
Sponsor's review
 
Internal Review
 |

[figure not shown]
| | |
|---|---|
|  | Statistical Analysis Plan |
| | Sponsor: Novartis Protocol: CRTH258AIT04 |

| Status and Version | Release Date | Change Description | Reason/Comment |

| 6.3.2. Secondary efficacy analysis | 36 |

Statistical Analysis Plan

| | |
|--|---|
| | Statistical Analysis Plan |
| | Sponsor: Novartis Protocol: CRTH258AIT04 |

LIST OF ABBREVIATIONS

| | |
|----------|--|
| AE | Adverse Event |
| AMD | Age-related Macular Degeneration |
| BCVA | Best-Corrected Visual acuity |
| CFP | Color Fundus Photography |
| CNV | Choroidal Neovascularization |
| COVID-19 | Coronavirus Disease 2019 |
| CRC | Central Reading Center |
| CRT | Central Retinal Thickness |
| CST | Central Subfield Thickness |
| DA | Disease Activity |
| DAA | Disease Activity Assessment |
| eCRF | Electronic Case Report Form |
| ELM | External Limiting Membrane |
| EOS | End-of-Study |
| EOT | End-of-Treatment |
| EQ-5D-5L | EuroQoL five dimensions and five levels |
| ETDRS | Early Treatment Diabetic Retinopathy Study |
| FA | Fluorescein Angiography |
| FAS | Full Analysis Set |
| HADS | Hospital Anxiety and Depression Scale |
| ICGA | IndoCyanine Green Angiography |
| IOI | IntraOcular Inflammation |

| | |
|--|----------------------------------|
| | Statistical Analysis Plan |
| | Sponsor: Novartis |
| | Protocol: CRTH258AIT04 |

| | |
|---------|--|
| IOP | IntraOcular Pressure |
| IRF | IntraRetinal Fluid |
| IVT | Intravitreal injection |
| LOCF | Last Observation Carried Forward |
| MedDRA | Medical dictionary for regulatory activities |
| OCT | Optical Coherence Tomography |
| OCTA | Optical Coherence Tomography |
| PCV | Polypoidal Choroidal Vasculopathy |
| PED | Pigment Epithelium Detachment |
| q8w | every 8 weeks |
| q12w | every 12 weeks |
| RPE | Retinal Pigment Epithelium |
| SAE | Serious Adverse Event |
| SAF | Safety Set |
| SAP | Statistical Analysis Plan |
| SD-OCT | Spectral Domain Optical Coherence Tomography |
| SHRM | Subretinal Hyperreflective Material |
| SmPC | Summary of Product Characteristics |
| SRF | Subretinal Fluid |
| sub-RPE | sub-Retinal Pigment Epithelium |
| UNG/P | Ungradable due to pathology |
| UNG/Q | Ungradable due to quality |
| VAS | Visual Analogue Scale |

| | |
|--|----------------------------------|
| | Statistical Analysis Plan |
| | Sponsor: Novartis |
| | Protocol: CRTH258AIT04 |

VEGF Vascular endothelial growth factor

wAMD wet Age-related Macular Degeneration

WHO World Health Organization

| | |
|--|---|
| | Statistical Analysis Plan |
| | Sponsor: Novartis Protocol: CRTH258AIT04 |

1. INTRODUCTION

This statistical analysis plan (SAP) is focused on the planned final analysis for the study CRTH258AIT04 based on the Protocol Version 02, dated November 11, 2021.

1.1. Changes from The Study Protocol

For SD-OCT parameters, in the study protocol, the Volume of Pigment-Epithelium Detachment (PEDs) defined as irregularly elevated lesions produced by the growth of the choroidal neovascular membrane and the accumulation of fluid or material in the sub-RPE space is planned to be evaluated as continuous variable (quantitative parameter). However, it was not possible to measure this volume according to the CRC evaluation. Consequently, the following qualitative parameters will be provided by CRC: the presence of PED will be summarized considering the possible values (i.e., 'No', 'Yes', 'UNG/P', 'UNG/Q') and in case of PED presence, a description of the type of PED will be provided considering the predominant feature as fibrovascular only, predominantly fibrovascular, purely serous, predominantly serous, drusenoid PED, UNG/P, UNG/Q.

Based on the study protocol, the primary endpoint should be analyzed according to Recursive Partitioning and Amalgamation (RECPAM) classification-tree analysis followed by multivariable logistic regression model. The RECPAM procedure was specified to evaluate interactions between imaging measurements assessed by OCT, OCTA, FA, ICGA and CFP and to identify distinct and homogeneous subgroups of participants in terms of q12w fluid-free participants at Week 48. This procedure should also have the aim to select the variables to be included in the multivariable logistic regression model and how to include them (for continuous, a threshold is identified during RECPAM). Based on data analyzed for the planned interim analysis, the image's grading of SD-OCT and mainly OCTA was affected by many ungradable values due to image's quality or due to pathology providing a great number of missing data that in RECPAM procedure cannot be managed. Moreover, the initial planned number of 263 enrolled patients wasn't reached, and the final number of 122 enrolled patient is too small for this type of the analysis. For these reasons, the RECPAM procedure will not be performed and in section 6.3.1 a different method to consider these variables in the multivariable logistic regression model and to choose them will be planned and explained. Moreover, the primary outcome will be considered as 'failure' also for patients who discontinued treatment during the study since for these patients the maintenance of a stable q12w regimen assigned at Week 16 up to Week 48 can not be observed and, thus, also these cases, will be considered as intercurrent event.

Moreover, in the primary analysis OCTA assessments planned in the study protocol will not be considered since based on interim analysis, it was observed that for these parameters most values will be missing.

| | |
|--|----------------------------------|
| | Statistical Analysis Plan |
| | Sponsor: Novartis |

Protocol: CRTH258AIT04

For what concern the LOCF approach reported in the study protocol, this approach will be maintained for the predictors to be included in the analysis of the primary endpoint since the focus is on the first visits (from baseline to Week 16) and all enrolled patients should perform these visits independently of treatment regimen that will be followed by each patient. For the secondary endpoints, LOCF approach will not be applied because after Week 16 each patient will have different scheduled of visits based on treatment regimen. The LOCF approach can be considered only until Week 16 but (1) for OCTA the number of missing data will lead to most data imputed than the one observed, (2) for SD-OCT the approach is applied in the analysis of primary endpoint, (3) for BCVA the LOCF approach will be provided until Week 16, (4) for HAD and EQ-5D-5L questionnaires the LOCF approach will not be applied since only two assessments of these questionnaires are planned in the study.

As performed for interim analysis, all analysis will be conducted on Safety population since during the interim analysis, in which all enrolled patients were considered (see section 6.6 for further details), the FAS and Safety populations include the same set of patients since per definitions of the study protocol, the FAS considered all enrolled patients who completed the baseline visit and all of them are treated and consequently all of them belong to Safety population.

The evaluation of prevalence of anxiety and depression will be performed only based on HAD questionnaire and not based in terms of treatment that patients could have received for anxiety/depression.

The following additional analysis will be included:

- SD-OCT parameters at baseline and type of predominant lesion will be also analyzed according to BCVA groups and CST groups based on changes at Week 12 in patients who performed Week 16 and were still on treatment at this timepoint.
- A graphical representation of BCVA ETDRS score and CST by means of spaghetti plot will be provided.
- Analyses on CST and BCVA will be also performed on patients with BCVA ETDRS score lower than 69 letters at baseline.

| | |
|--|----------------------------------|
| | Statistical Analysis Plan |
| | Sponsor: Novartis |
| | Protocol: CRTH258AIT04 |

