1.2 Purpose

The purpose of this phase IV study is to identify innovative early imaging parameters as predictors of the long-term clinical response to brolucizumab in terms of fluid resolution in patients with wAMD with the purpose to evaluate their potential in supporting the treatment regimen choice (q12w or q8w).

2 Objectives and endpoints

Table 2-1 Objectives and related endpoints

Objective(s)	Endpoint(s)
Primary Objective The primary objective is to assess the predictive value of early anatomical parameters measured by multimodal imaging from Baseline to Week 16, in brolucizumab-treated participants with wAMD who present fluid resolution (i.e. absence of IRF and SRF) at Week 48 and have maintained the q12w treatment regimen up to Week 48 after the loading phase, defined also as fluid-free response (q12w fluid-free participants), compared with participants under a more frequent regimen and/or not fluid-free at Week 48.	Endpoint(s) for primary objective Early predictive factors of fluid-free response, which is defined as the absence of IRF and SRF (assessed by SD-OCT) at Week 48 in patients with a stable q12w treatment regimen up to Week 48 after the loading phase. The variables considered as potential predictive factors in the statistical model will be selected among the following qualitative and quantitative anatomical parameters: 
1. Basal CNV lesion type, as assessed by SD-OCT at Baseline and FA, ICGA and CFP at Screening2. Parameters assessed by OCTA at each visit from Baseline to Week 16, of which the main are presence/absence of branching vessels, peripheral anastomotic arcades, vascular loops and dark halo, and quantification of CNV flow size and vessel density3. Parameters assessed by SD-OCT at each visit from Baseline to Week 16, of which the main are presence/absence of sub-RPE fluid,

Objective(s)	Endpoint(s)
	subretinal hyperreflective material (SHRM), outer retinal tubulation, status of the External Limiting Membrane (ELM) and measurement of central retinal thickness (CRT) and PED volume.
Secondary Objective(s)	Endpoint(s) for secondary objective(s)

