3.5. Sample Size and Power Estimation

The sample size calculation is based on the assumption of an expected percentage of participants who have maintained the q12w regimen up to Week 48 equal to 56%, as derived from the HAWK study, and the hypothesis of a maximum percentage of not-fluid free participants out of these q12w-regimen participants at Week 48 equal to 18%. Therefore, the percentage of responders, defined as fluid-free participants who have maintained a q12w stable regimen up to Week 48, could range between 56% to 46%.

[figure not shown]
Considering a percentage of responders of 56% and a maximum width of the 95% confidence interval of 12%, 263 patients should be enrolled. Applying the rules of thumb, with 263 patients and a percentage of responders of 56%, a maximum number of 12 covariates can be included in the multivariate regression model (Harrell, 2015). As shown in Figure 2.5-1, the precision of the estimate remains stable around 12%, considering a percentage of responders ranging between 56% to 46%. Similar considerations can be made with a number of covariates that remains equal to 12.

Finally, to account for a screening failure rate of 12%, a total of approximately 300 participants should be screened in order to enroll 263 evaluable participants.

The sample size calculations were performed with nQuery 7.0.

| | |
|--|----------------------------------|
| | Statistical Analysis Plan |
| | Sponsor: Novartis |
| | Protocol: CRTH258AIT04 |

[figure not shown]
Figure 2.5-1: Precision of the estimate scenario

Since the enrolment was closed with less than 263 enrolled patients, the precision of the 95% CI will be re-computed based on the effective number of patients evaluable for the primary endpoint of the study.

Based on interim analysis, 122 enrolled patients will be available and consequently, the Figure above is recomputed according to the effective number of enrolled patients and provided below in Figure 2.5-2:

Figure 2.5-2: Precision of the estimate scenario re-computed

Based on different scenario of expected proportion between 46% to 56% and the effective number of 122 enrolled patients, the maximum width that can be observed will be of 17.74%.

| | |
|--|---|
| | Statistical Analysis Plan |
| | Sponsor: Novartis Protocol: CRTH258AIT04 |

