4. DEFINITIONS AND GENERAL METHODOLOGY

4.1. General Methodology

Statistical tables, listings and analyses will be produced using SAS® release 9.4 (64 bit) or later (SAS Institute, Inc., Cary, NC, USA).

The data from all sites will be pooled and summarized.

Continuous data will be summarized with mean, standard deviation (SD), median, Q1, Q3, minimum and maximum. Categorical data will be presented by absolute and relative frequencies (n and %) or contingency tables. The percentage calculation will be based on total values (i.e., count will be shown also in the missing category, unless otherwise specified).

Unless stated otherwise, a two-sided alpha level 0.05 will be considered. No alpha level adjustment will be carried out for primary and secondary outcome variables, unless otherwise specified.

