- **Non-ocular medical and surgical history** will be summarized by System Organ Class and Preferred Term according to the MedDRA dictionary, presenting the number and percentage of patients with at least one non-ocular medical and surgical history finding (i.e., reported in the non-ocular medical history category of MEDICAL HISTORY/CURRENT MEDICAL CONDITIONS eCRF page) considering separately relevant medical/surgical history, i.e. conditions reported as 'Not ongoing', and current medical/ surgical condition, i.e. conditions reported as 'Ongoing'.
- **Fluorescein Angiography (FA) at screening** will be described considering the following parameters assessed in the study eye:
 - **Total lesion size:** the lesion associated with CNV will be described reporting the proportion of patients for whom the area is 'Evaluable' (i.e., the numeric measure should be present), 'Cannot grade (unreadable)', 'Not available (missing FA)' or 'Not applicable (=absent/no CNV)'. For patients with evaluable measurement, the area of lesion associated with CNV (mm²) will be summarized with descriptive statistics for continuous data.
 - **Total CNV size:** the CNV within a lesion will be described reporting the proportion of patients for whom the area is 'Evaluable' (i.e., the numeric measure should be present), 'Cannot grade (unreadable)', 'Not available (missing FA)' or 'Not applicable (=absent/no CNV)'. For patients with evaluable measurement, the area of CNV within a lesion (mm²) will be summarized with descriptive statistics for continuous data.

The proportion of patients who performed the FA imaging also in the fellow eye will be provided even if these parameters will not grade.

A description for the FA imagines' quality will be also provided reporting the proportion of images with quality concerns present and a description of the issue detected that could be one or more of the following:

- NOT PER PROTOCOL
- POOR FOCUS
- POOR CONTRAST
- UNDEREXPOSED
- OVEREXPOSED
- POOR FIELD PLACEMENT
- NO TIMER INFORMATION
- OTHER/ADDITIONAL DETAILS

Similarly, the proportion of imagines with quality concerns that prevent any grading is provided together with the issue(s) detected (one or more than one among the list previously described).

| | |
|--|---|
| | Statistical Analysis Plan |
| | Sponsor: Novartis Protocol: CRTH258AIT04 |

- **Color Fundus Photography (CFP) at screening** will be described considering the following qualitative parameters assessed in the study eye:

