NA=Not Applicable; CNV=Choroidal Neovascularization; UNG/P=Ungradable due to pathology; UNG/Q=Ungradable due to quality SHRM=Subretinal hyper reflective materia; ORT=Outer retinal tubulation; ELM=External Limiting Membrane; CST=Center Subfield Thickness; PED=Pigment Epithelial Detachment.

Of note, for each variable 'Missing' values can be present in case that images are collected but not graded by Central Reading Center (CRC) since they are collected by means of a not certificated instrument.

| | |
|--|----------------------------------|
| | Statistical Analysis Plan |
| | Sponsor: Novartis |
| | Protocol: CRTH258AIT04 |

Analysis methodology

Firstly, the proportion of patients with and without q12w fluid-free will be provided and then a descriptive summary table by q12w fluid-free and not q12w fluid-free will be provided for each variables described in table above.

A logistic models will be performed for each one of the variables listed above considering as outcome the patients' classification in q12w fluid-free and not q12w fluid-free.

Multivariable logistic model will be performed considering as outcome the patients' classification in q12w fluid-free and not q12w fluid-free and as covariates all the variables with $p<0.10$ in the previous analysis. Results of logistic models will be presented in terms of beta coefficient and standard error, Odds Ratio and relative 95% Confidence interval and p-value.

All these analyses will be performed on Safety population.

Data handling rules

In case of patients who dropped out at any time after baseline, the primary outcome cannot be evaluated since the patient status related to treatment regimen and presence of IRF o SRF at Week 48 are not observed. The dropped-out patients constitute intercurrent event and they will be considered a not q12w fluid-free at Week 48. Similarly, in case of patients who discontinued the treatment at any time after baseline, the primary outcome cannot be totally evaluated since the patient treatment regimen at q12w cannot be observed until Week 48. The patients who discontinued treatment constitute intercurrent event and they will be considered a not q12w fluid-free at Week 48.

Sensitivity of primary analysis

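### The SAP leaves OCTA out of every analysis of predictors of q12w fluid-free response, including the one-variable steps that could use the gradable values, so the protocol's question on OCTA gets no estimate.

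*SAP*

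**What the plan says.** Protocol Table 2-1 lists three groups of candidate predictors for the primary endpoint: basal CNV lesion type, SD-OCT parameters and "Parameters assessed by OCTA at each visit from Baseline to Week 16". Protocol 12.4.1 repeats the list.

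SAP 1.1 changes this: "in the primary analysis OCTA assessments planned in the study protocol will not be considered since based on interim analysis", most values of these parameters are expected to be missing. The same section says that RECPAM cannot handle the amount of missing data, and that carrying the last observation forward would impute more OCTA values than were observed.

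The predictor table in SAP 6.3.1 contains CNV lesion type and SD-OCT variables only. Three steps draw on it: a descriptive table by response status, the one-variable step ("A logistic models will be performed for each one of the variables listed above considering as outcome" response status), and a multivariable model of the variables with p<0.10.

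SAP 6.3.2.1 keeps OCTA as a secondary analysis. It gives image quality and every parameter by visit, with changes from baseline and paired or McNemar tests, all on observed data. SAP 6.3.2.5 includes OCTA as a covariate category in the Week 16 regimen-choice model. That covariate records whether the investigator used OCTA, and the outcome is the regimen chosen.

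**The concern.** The by-outcome table and the one-variable models take one predictor at a time. A sparse OCTA variable there removes no patient from the analysis of any other predictor. The SAP already treats gradable OCTA values as fit for testing against baseline, and gives no separate reason for not setting the same values against response.

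OCTA is prominent in the protocol's rationale. Section 1.1 says that no trial has prospectively studied early OCTA and SD-OCT parameters as predictors of response to brolucizumab. Section 4.1 presents OCTA as potentially relevant to the regimen decision. Table 8-1 schedules it at every visit. As planned, a reader of the results would learn how OCTA features changed over time, but not whether any of them differed between responders and non-responders, even descriptively.

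**Working it through.** **1. The plan's own figures.** SAP 3.5 states: "Considering a percentage of responders of 56% and a maximum width of the 95% confidence interval of 12%, 263 patients should be enrolled". With n = 1.96² × p(1−p) / (w/2)², this gives 1.96² × 0.56 × 0.44 / 0.06² = 262.9, so 263 is reproduced. At N = 122 the full width 2 × 1.96 × √(p(1−p)/N) is 17.62% at p = 0.56, 17.74% at 0.50 and 17.69% at 0.46, so the stated maximum of 17.74% is reproduced. No stated figure is in dispute.

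**2. Room in the joint model.** SAP 3.5 says that "a maximum number of 12 covariates can be included in the multivariate regression model" at N = 263. Ten patients in the smaller outcome class per covariate gives 0.44 × 263 / 10 = 11.6, consistent with 12. At N = 122 it gives 0.44 × 122 / 10 = 5.4 at 56% responders and 0.46 × 122 / 10 = 5.6 at 46%, so about five. Complete-case loss makes this worse. Three OCTA variables, each gradable in half the eyes, would leave 122 × 0.5³ = 15 patients if gradability were independent, and at most 61 if the same eyes were gradable throughout. Keeping OCTA out of the multivariable model is sound.

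**3. What one-variable models could deliver.** Inputs and assumptions:
- 122 enrolled (SAP 1.1).
- "a two-sided alpha level 0.05 will be considered" (SAP 4.1).
- A responder share that "could range between 56% to 46" percent (SAP 3.5), assumed to hold among gradable eyes.
- Gradable eyes m: not given. A majority missing is read as fewer than 61 of 122, and m is varied from 60 down to 24.
- A binary feature present in half the eyes, or a continuous feature per SD.

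Formulas:
- CI factor for a binary feature: exp(1.96 × √(4 / (m p(1−p)))). At p = 0.50 this is exp(1.96 × √(16/m)): 2.8 at m = 60, 3.0 at 50, 3.5 at 40 and 4.2 at 30.
- Odds ratio per SD at 80% power: exp((1.96 + 0.84) / √(m p(1−p))).
- Binary odds ratio at 80% power: normal approximation for two proportions. For m = 61 and p = 0.56, response of 0.735 against 0.385 gives 80% power, and (0.735/0.265) / (0.385/0.615) = 4.4.

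Results over 46–56% responders:

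| Gradable eyes | Smaller outcome class | 95% CI factor, binary | Binary OR at 80% power | OR per SD at 80% power |
|---|---|---|---|---|
| 122 (none missing) | 54–56 | 2.0 | 2.8 | 1.7 |
| 60 | 26–28 | 2.8 | 4.4–4.5 | 2.1 |
| 49 | 22–23 | 3.1 | 5.3 | 2.2 |
| 37 | 16–17 | 3.6–3.7 | 6.9–7.0 | 2.5 |
| 24 | 11 | 5.0 | 11.8–12.1 | 3.2 |

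The smaller class stays above 10 throughout, so a model with one parameter can be fitted at every m shown, but with little precision.

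**4. Which OCTA parameters have a baseline grade.** Under SAP 6.3.2.1, dark halo, vascular loops, peripheral anastomotic arcades, lesion area, greatest linear diameter and vascular density can be graded at Baseline. The last three are graded only when a CNV lesion is seen, which lowers their count further. Branching vessels is graded against the previous read and has no baseline value.

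**The case against.** The strongest reply is that the SAP gives OCTA its own reason, separate from the RECPAM one, and that this reason acts parameter by parameter. Sparse values weaken a one-variable model too. Since repeated predictors in SAP 6.3.1 are built from baseline-to-last change, OCTA variables built that way would suffer more. Part of the ungradability is due to pathology, so the gradable eyes are a selected group. The change is also declared in SAP 1.1 and carried through consistently. All of this stands. It supports an exploratory label and the use of baseline values as observed. It does not explain why no summary by response is given.

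Four stronger readings are tempting, and the documents do not support them:
- A reader might infer that missingness is an obstacle only for the joint model. The table above shows the cost for single variables.
- A reader might infer that OCTA goes unused, or that the trial says nothing on innovative biomarkers. OCTA remains a secondary endpoint and a category in the regimen-choice model. Protocol 1.1 counts SD-OCT among the innovative parameters, and it stays in the primary model.
- A reader might infer that one-variable models would settle odds ratios of 3 to 4. At 40 eyes an estimate of 1 has an upper limit of about 3.5 and does not exclude 3. At 30 eyes an estimate of 4 has a lower limit of 4/4.2, below 1.
- A reader might take the FA measure in SAP 6.2, where "the CNV within a lesion will be described reporting the proportion of patients for whom the area is" evaluable, as a replacement. The protocol's predictor is CNV flow size on OCTA. FA enters the protocol's predictor list only through lesion type.

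**Conclusion.** The point holds as a gap in the scope of the analysis. No planned analysis relates a graded OCTA finding to q12w fluid-free response, although the protocol makes this part of the primary objective and the SAP finds the same values usable elsewhere. No figure is wrong and no bias in the planned SD-OCT results is shown.

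What can be recovered is modest. With fewer than 61 gradable eyes, the 95% interval of a binary odds ratio spans a factor of at least about 2.8 each way (4.2 at 30 eyes), and 80% power needs an odds ratio of about 4.4 or more. These figures rest on an assumed gradable count, a feature present in half the eyes and 46–56% responders. A less balanced feature would do worse. The results could only be exploratory, but they would be a partial answer where the plan now gives none.

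**What to change.** In SAP 6.3.1, keep OCTA out of the multivariable model and add an exploratory observed-case table by q12w fluid-free status. Include the six parameters that can have a baseline grade (dark halo, vascular loops, peripheral anastomotic arcades, CNV lesion area, greatest linear diameter, vascular density) and leave out branching vessels. For each, give the number of gradable eyes and a one-variable odds ratio with 95% CI.

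Report the gradable and ungradable shares by outcome, noting that ungradability mixes pathology, image quality and device (SAP 6.3.1 notes that images from non-certified instruments are not graded). Label everything as exploratory, unadjusted for multiplicity and drawn from a selected subset. State in the conclusions that OCTA was not assessed in the primary model. Screening CNV size on FA may be added as an option, but not as a substitute for OCTA CNV flow size.

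The cost is a few outputs on data already graded. The downside is wide intervals in a selected subset and six more unadjusted comparisons: if none of the six is related to response, 6 × 0.05 = 0.3 intervals would be expected to exclude 1 by chance.
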